7. PLANNED ANALYSIS

The labelling and display format of statistical parameters will follow BI standards [10]. For End-Of-Text tables, the set of summary statistics is: N, Mean, SD, Min, Q1 (lower quartile), Median, Q3 (upper quartile) and Max. In descriptive statistics tables, all statistical parameters will be rounded to one additional digit than the raw individual value.

Tabulations of frequencies for categorical and ordinal data will include all possible categories and will display the number of observations in a category as well as the percentage (%) relative to the respective group (unless otherwise specified, all subjects in the respective subject set whether they have non-missing values or not). The category missing will be displayed only if there are actually missing values. Percentages will be rounded to one decimal place.

Subject sets for the planned analyses are displayed in Table 6.3: 2. Subject data listings (SDLs) will be based on the Observed subjects set.

If applicable, conversion from days to weeks, months and years will be as follows:

- Weeks = Days / 7
- Months = (Days * 12) / 365.25
- Years = Days / 365.25

Descriptive statistics will be presented, using both the OBS and PPSBM subject analysis sets, for the following demographic and baseline characteristics, by diagnosis group and for all COPD GOLD groups combined (GOLD 1-3). A1ATD group will be presented separately. See Section 6.7 for definition of baseline measures.

Subjects who have not prematurely discontinued the study should be displayed as "Still in study". Subjects who completed week 104 and didn't consent for the 3rd year expansion of the observational period, they will be displayed as "Completers".

Demographic data: Sex, ethnicity, race, age (years), age (categories), height [cm], weight [kg] and BMI [kg/m²].

Disease characteristics:

- Smoking history in pack years
- Subgroups defined in Section 6.3
- Medical history for COPD (by type of medical disorder)
- Symptom questionnaires: defined in Section 5.3.4

- Spirometry: parameters listed in Section 5.3.1.1
- Body plethysmography: parameters listed in Section 5.3.1.2
- DLCO: parameters listed in Section 5.3.1.3
- SpO2 [%]
- BODE index
- 6 minute walk test: parameters listed in Section 5.3.7.3
- Soluble biomarkers: parameters listed in Section 5.3.2
- biomarkers:
 - Qualitative and Quantitative CT:

7.2 CONCOMITANT DISEASES AND MEDICATION

Only descriptive analysis is planned for this section of the report, using the PPSBM subject analysis set.

Concomitant medication taken at baseline or during the observation period will be summarised by World Health Organization-Drug Dictionary (WHO-DD) name and preferred term (PT), and presented by subject group.

Previous concomitant medication, i.e. those taken and stopped prior to entering the observation period, will be listed only.

Baseline conditions / concomitant diagnoses will be summarised by Medical Dictionary for Regulatory Activities (MedDRA) system organ class (SOC) and PT, and presented by diagnosis group.

All data will be coded using the most recent versions of WHO-DD and MedDRA dictionaries.

7.3 TREATMENT COMPLIANCE

Not applicable.

7.4 PRIMARY ENDPOINT(S)

7.4.1 Primary analysis

Primary analysis will be performed on per protocol set – biomarker subjects (PPSBM).

Absolute change in lung density decline based on PD15 adjusted for lung volume (ALD) [g/L/year] (up to week 156)

The change from baseline over time for PD15 adjusted for lung volume (ALD) will be evaluated with a restricted maximum likelihood (REML) based mixed model for repeated measures (MMRM) approach with the fixed, categorical effects of subject groups (SG) at each visit. Visit (weeks) will be treated as the repeated measure with an unstructured covariance structure used to model the within-patient measurements.

The statistical model will be as follows:

$$y_{ijk} = \tau_{jk} + e_{ik} , e_{ik} \sim N(0, \sigma^2)$$

[figure not shown]
 y_{ijk} = change from baseline for ALD for subject i in subject-group (SG) j at visit k, k = 5, 6, 7

 τ_{jk} = the fixed effect subject-group (SG) j at visit k, j=0,...,4

The subject-group indicator is defined as:

$$SG = \begin{cases} 0, & \text{Ex} - \text{smoking control (reference category)} \\ 1, & \text{COPD GOLD 1} \\ 2, & \text{COPD GOLD 2} \\ 3, & \text{COPD GOLD 3} \\ 4, & \text{COPD} + \text{A1ATD} \end{cases}$$

The Kenward-Roger approximation will be used to estimate denominator degrees of freedom and adjust standard errors. Significance tests will be based on least-squares means using a two-sided $\alpha = 0.05$ (two-sided 95% confidence intervals).

Annual rate of lung function decline based on FEV1 [L/year] (up to week 156)

The continuous outcome measure FEV1 [L] will be analysed by performing a restricted maximum likelihood (REML) based approach using a random slope and intercept model. The analysis will include the fixed, categorical effect of subject-group indicator (SG, as specified above), and the fixed continuous effects of 'time' as well as the SG-by-time interactions. Random effects will be included for patient response for both time and intercept.

The statistical model will be as follows:

$$y_{ijk} = (a + a_i + \tau_j) + (\gamma + g_i + \varphi_j)t_{ik} + e_{ik} ,$$

$$iid$$

$$(a_i, g_i) \sim N_2(\mathbf{0}, \mathbf{\Sigma}), e_{ik} \sim N(0, \sigma^2)$$

 y_{ijk} = response variable (FEV1 [L]) for subject i in at visit k belonging to SG j,

 α = mean patient intercept

 a_i = random intercept effect for subject i, i=1,2,...

 τ_i = intercept coefficient of the effect of subject-group j, j=0, 1, 2, 3, 4

 γ = mean patient slope

 g_i = random slope effect for subject i

 φ_i = slope coefficient of the effect of SG j

 t_{ik} = time of measurement k for subject i, k= 1, 2,... 7

 e_{ik} = the random error associated with the kth visit of the ith subject. Errors are independent and normally distributed with mean 0 and variance σ^2 , and uncorrelated with a_i and g_i .

 Σ = a 2x2 unstructured covariance matrix

The Kenward-Roger approximation will be used to estimate denominator degrees of freedom and adjust standard errors. Significance tests will be based on least-squares means using a two-sided $\alpha = 0.05$ (two-sided 95% confidence intervals). The primary subject-group comparison of slopes will be assessed through the SG-by time interaction coefficient.

SAS procedure PROC MIXED is implemented for this analysis. SAS code can be found in Section 9.5.2.

Number of exacerbations during study (up to week 156)

This endpoint will be summarized descriptively by the following categories: 0 vs. 1 vs. \geq 2.

Duration of exacerbations during study [days] (up to week 156)

This endpoint will be calculated by the sum of episodes during the study and will be summarized descriptively. Duration of exacerbations will be summarized for subjects with at least one exacerbation.

Occurrence of an at least moderate exacerbation during study (up to week 156)

This endpoint will be summarized by the number of patients with an at least moderate exacerbation during study falling into the following categories 0 vs. 1 vs. \geq 2.

Occurrence of a severe exacerbation during study (up to week 156)

This endpoint will be summarized by the number of patients with a severe exacerbation during study falling into the following categories $0 \text{ vs. } 1 \text{ vs. } \ge 2.$

Definitions of severity of exacerbations can be found in Section 5.7.1.1 of the CSP.

[figure not shown]

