7. STATISTICAL METHODS AND DETERMINATION OF SAMPLE SIZE

7.1 STATISTICAL DESIGN - MODEL

[REDACTED]

[REDACTED]

All subjects entering the study will be included in the analyses. Protocol violations will be defined in TSAP. Per-protocol set will be defined accordingly thereafter.

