7.3.4 Safety analyses

All subjects enrolled will be included in the safety analysis. In general, safety analyses are descriptive in nature and are based on BI standards. No hypothesis testing is planned. Adverse events (AEs) will be coded using the latest version (at the time of database lock) of Medical Dictionary for Regulatory Activities (MedDRA) coding dictionary. Standard BI summary tables and listings will be produced by subject groups.

Statistical analysis and reporting of AEs will focus on AEs that are study procedure related as judged by the investigators and medical events of special interest (MESI) as defined in [Section 5.7.](#)

Frequency, severity, and causal relationship of AEs will be tabulated by system organ class and preferred term after coding according to the latest version of MedDRA. Frequency of MESIs will be tabulated by disorder.

Laboratory data will be analyzed both quantitatively as well as qualitatively. The latter are done via comparison of laboratory data to their reference ranges. Values outside the reference range as well as values defined as clinically relevant will be highlighted in the listings.

Subject groups will be compared descriptively with regard to distribution parameters as well as with regard to frequency and percentage of patients with abnormal values or clinically relevant abnormal values.

Vital signs, physical examinations, or other safety-relevant data observed at screening, baseline, during the course of the study and at the end-of-study evaluation will be assessed with regard to possible changes compared to findings before start of treatment.

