4.2 CHANGES

There were no changes to the planned analyses as compared to what was described in the CSP. However, the structure of the planned analyses in the TSAP is not consistent to Section 7 of the CSP. This change was necessary to allow for a better understanding of order and importance of the conducted analyses.

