6.3 SUBJECT SETS ANALYSED

The following subject sets are planned to be investigated:

Table 6.3: 1 Definition of populations

Analysis Population	Definition
Screened subjects set (SCR)	All subjects enrolled in the study, following the receipt of informed consent.
Observed subjects set (OBS)	All subjects, from the SCR, who are eligible to enter the observation period.
Per-protocol set (biomarker subjects) (PPSBM)	All subjects, from the OBS, who have no IPDs affecting the clinical or biomarker assessments.
MRI set	All subjects, from the PPSBM, with MRI performed at baseline

Table 6.3:2 shows which analysis set is used for each class of assessment:

[figure not shown]
Table 6.3: 2 Subject sets for planned analyses

Planned analysis	Subject set
Disposition	Screened subjects set
Demographic data	Observed subjects set
	Per-protocol set (biomarker subjects)
Clinical and biomarker assessments	Per-protocol set (biomarker subjects)
Safety analyses	Observed subjects set

[figure not shown]
All analyses will be performed on observed cases (OC). Note that the number of subjects with available data for an assessment may differ. For details, see Section 6.6 "Handling of missing data".

TSAP for BI Study No: 352.2069 Proprietary confidential information © 2022 Boehringer Ingelheim International GmbH or one or more of its affiliated companies

TSAP for BI Study No: 352.2069 Proprietary confidential information © 2022 Boehringer Ingelheim International GmbH or one or more of its affiliated companies

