7.9 MEDICAL EVENTS OF SPECIAL INTEREST (MESIS)

Specific disorders related to the underlying COPD disease as defined in the CSP, Section 5.7, will be collected during the study. MESI are analysed per AE standards based on PPSBM subjects. The frequencies of these MESIs will be summarised by disorder and intensity following the same order as in the eCRF. A separate listing by subject group and disorder will be created including additional information of start/end date, outcome, provided therapy, and intensity of the event.

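### MESI frequencies move from the protocol's all-enrolled safety analysis to the per-protocol set, and SAP 4.2 declares neither this nor the set used for the six main outcomes

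*SAP*

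**What the plan says.** **MESI.** Protocol 7.3.4 (Safety analyses) says "All subjects enrolled will be included in the safety analysis". The same subsection names MESI, next to procedure-related events, as one of two focuses of adverse-event reporting, and asks for MESI frequency by disorder. SAP 7.9 says "MESI are analysed per AE standards based on PPSBM subjects", with frequencies by disorder and intensity. SAP 7.8.1 to 7.8.5 use OBS for adverse events, laboratory data, vital signs, ECG and physical examination.

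**Main outcomes.** Protocol 7.1 says "All subjects entering the study will be included in the analyses". It leaves protocol violations to the SAP and adds "Per-protocol set will be defined accordingly thereafter". SAP Table 6.3:1 defines PPSBM as "All subjects, from the OBS, who have no IPDs affecting the clinical or biomarker assessments". Table 6.3:2 gives PPSBM alone for the row "Clinical and biomarker assessments", but both OBS and PPSBM for demographic data. SAP 7.4.1 opens with "Primary analysis will be performed on per protocol set". Under that heading it covers the six outcomes of SAP 5.1: change in adjusted lung density, FEV1 decline and four exacerbation outcomes.

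**Disclosure.** SAP 4.2 says "There were no changes to the planned analyses as compared to what was described in the CSP" and then admits only a difference in structure from protocol section 7. SAP 4.1, SAP 4.3 and the visible history table do not mention the analysis set. The history table records that MESI received their own section, not that their population differs from protocol 7.3.4.

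**The concern.** Adverse events are collected only if they are associated with a study procedure (protocol 5.9.6.2, SAP 7.8.1). Events such as pneumonia or heart failure are therefore counted, as far as visible, only in the MESI table. A subject with an entry deviation who is nevertheless followed for up to 156 weeks contributes to the adverse-event, laboratory and vital-sign tables but not to this one. Some excluding codes are respiratory and could plausibly be related to later respiratory events: recent respiratory infection (A2.02), hospitalisation for respiratory failure (A2.11), bronchiectasis (A2.13) and a screening visit soon after an exacerbation (F1).

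For the main outcomes, SAP 4.2 gives no hint that the set was narrowed or specified beyond protocol 7.1. The only visible set depends on a deviation list that SAP 6.2 calls a working list, possibly open until the report planning or database lock meeting (DBLM). Without a second set beside it, a reader cannot see whether those late decisions matter.

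**Working it through.** **Step 1: the sets side by side.** Protocol 3.3 treats enrolled subjects as those who have signed informed consent. That is the SAP's screened set (SCR), and the SAP sets are nested: SCR contains OBS, which contains PPSBM.

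| Analysis | Protocol | SAP |
|---|---|---|
| Procedure-related adverse events | all enrolled (7.3.4) | OBS (7.8.1); events in screening failures handled separately (7.8) |
| Laboratory, vital signs, physical examination | all enrolled (7.3.4) | OBS (7.8.2, 7.8.3, 7.8.5) |
| MESI frequency | all enrolled (7.3.4) | PPSBM (7.9) |
| Demographic and baseline data | no set named | OBS and PPSBM (Table 6.3:2, section 7) |
| Six main outcomes | all subjects entering (7.1); per-protocol set foreseen, no visible use assigned | PPSBM only, as far as visible (Table 6.3:2, 7.4.1) |

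MESI is the only item of protocol 7.3.4 in this table that goes to PPSBM.

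**Step 2: what removes a subject from PPSBM.** Codes marked PPSBM in SAP Table 6.2:1 are 8 in A1, 15 in A2, 2 in D2, F1 and Z1: 8 + 15 + 2 + 1 + 1 = 27. (B1, no consent, removes a subject from every set and is not counted.) All but Z1, that is 26, concern entry or screening. Codes left to medical judgement at the DBLM are 13 in A2, D2.01, D2.02, F1 and Z1: 13 + 2 + 1 + 1 = 17. Three more (A1.06, A1.07, A1.10) are settled there on genotype data. Restarted smoking (G1), restricted medication during observation or before lung function testing (D2.03, D2.04) and COVID-related missed examinations or visits (Q1, Q2) exclude nobody.

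**Step 3: how far the MESI table could move.** The documents give no exclusion rate and no MESI rate in excluded subjects, so both are assumptions. Let e be the fraction of OBS excluded from PPSBM and RR the ratio of MESI frequency in excluded to retained subjects. Then

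OBS frequency = PPSBM frequency × [1 + e(RR − 1)]

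relative shortfall of the PPSBM table = 1 − 1/[1 + e(RR − 1)]

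| Assumed e | Subjects, of up to 455 | RR = 1 | RR = 2 | RR = 3 |
|---|---|---|---|---|
| 2% | 455 × 0.02 ≈ 9 | 0% | 1 − 1/1.02 = 2.0% | 1 − 1/1.04 = 3.8% |
| 5% | 455 × 0.05 ≈ 23 | 0% | 1 − 1/1.05 = 4.8% | 1 − 1/1.10 = 9.1% |
| 10% | 455 × 0.10 ≈ 46 | 0% | 1 − 1/1.10 = 9.1% | 1 − 1/1.20 = 16.7% |

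An RR below 1 reverses the sign. The table shows sensitivity only and is not a forecast.

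**Step 4: sample size.** The protocol's basis, 125 × (1 − 0.20) = 100 per COPD group (7.7), allows for dropout only. Without an exclusion rate no further calculation is justified.

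**The case against.** The protocol is not uniform on MESI. The synopsis, 5.1.2 and 7.3 list them apart from safety assessments, so SAP 7.9 can be read as following the "Clinical and biomarker assessments" row. This explains the choice but does not reconcile it with 7.3.4. Subject data listings are on OBS (SAP 7), so excluded subjects' events need not vanish from the report. That stands, but a listing is not a frequency table. OBS would not reproduce 7.3.4 exactly either, because enrolled means consented and MESI are captured from consent onwards (protocol 5.7). That also stands and shapes the fix.

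A reader might infer three stronger things.

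- **That the SAP overrode an all-subjects primary analysis, or has no OBS analysis at all.** The documents do not show this. Protocol 7.1 leaves violations and the per-protocol set to the SAP without saying which analyses use it, and part of 7.1 is redacted. SAP pages between 7.5.2 and 7.7, text after Table 6.3:2 and most of section 9 are not shown.
- **That PPSBM selects on outcome or breaches an intention-to-treat principle.** The study is not randomised and has no confirmatory hypothesis (protocol 7.2, 7.6). Nearly all excluding codes are entry or screening criteria. Several remove subjects who would blur the group contrasts: controls without normal lung function (A1.04, A1.05), subjects without COPD (A1.06) and wrong genotypes (A1.10, A2.21).
- **That power or precision is lost.** No exclusion rate is given, 20% is an upper limit for dropout, and the mixed models in SAP 7.4.1 use the available visits of subjects who leave early.

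**Conclusion.** The point holds as one of table completeness and transparency. The MESI part is the firmer: protocol 7.3.4 and SAP 7.9 name different populations for the same table, the SAP's other safety analyses use OBS, and SAP 4.2 does not mention the difference. The main-outcome part is milder. PPSBM is a reasonable main set for an exploratory study of defined diagnosis groups. However, its use as the only visible set is not declared, and 17 of its 27 excluding codes, including the open-ended Z1, are decided by judgement at the DBLM.

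The size cannot be determined. Eligibility criteria applying at Visit 2 are re-checked before that visit proceeds (protocol 6.2.2), so OBS and PPSBM may differ little. If excluded subjects have MESI as often as the others, the frequencies do not change. The conclusion rests on visible text only; hidden text could already contain an OBS analysis of the main outcomes.

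**What to change.** 1. In SAP 7.9, tabulate MESI on OBS, in line with the other SAP safety tables. List MESI in screening failures separately, as SAP 7.8 already does for adverse events, because OBS is narrower than the protocol's enrolled population.
2. Unless text not shown already does so, report the six main outcomes on OBS with the same models and summaries, as a supportive analysis beside PPSBM. The SAP already shows demographic and baseline data on both sets.
3. In SAP 4.2, state the sets used for MESI, safety and main outcomes as differences from, or specifications of, protocol 7.1 and 7.3.4.

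The cost is a few sentences in the SAP, reruns of existing programs on a second set and some extra output. The supportive OBS estimates may be slightly noisier because they include ineligible subjects. All PPSBM results for the main outcomes are kept.

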4.3 CLARIFICATIONS

This TSAP provides clarification on main outcomes listed in CSP Section 5.1.1. A more precise definition is provided in Section 5.1.

The terms "assessment(s)", "endpoint(s)" and "outcome(s)" as well as the term "subject(s)" and "patient(s)" will be used interchangeably within this document.

The description 'ex-smoking controls' will be used in analysis outputs instead of 'Healthy subjects' to characterise better this type of population.

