5. ENDPOINT(S)

Whenever applicable, the following variables are defined for all continuous assessments. Change from baseline always refers to the absolute changes, unless otherwise specified.

- Observed values at baseline and at each post-baseline visit
- Change from baseline (CfB) at each post-baseline visit, defined as

 $CfB_k = post-baseline value at visit k - baseline value$

Relative change from baseline (rCfB) at each post-baseline visit, defined as
 rCfB_k = (post-baseline value at visit k – baseline value) / (baseline value) x100

Unless otherwise specified, these variables are summarized and analysed.

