5.1 PRIMARY ENDPOINT(S)

The main outcome measures of the study are described in CSP Section 5.1.1. To clarify the CSP wording, the main outcomes are also listed here:

- Absolute change from baseline in lung density based on PD15 adjusted for lung volume (ALD) [g/L/year] (up to week 156) (for definition of ALD see Section 9.2)
- Annual rate of lung function decline based on FEV1 [mL/year] (up to week 156)
- Number of exacerbations during study (up to week 156)
- Duration of exacerbations during study [days] (up to week 156)
- Occurrence of an at least moderate exacerbation during study (up to week 156)
- Occurrence of a severe exacerbation during study (up to week 156)

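### The main lung-density outcome is labelled g/L/year in SAP 5.1 and 7.4.1, but the printed model estimates undivided change from baseline at Weeks 52, 104 and 156

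*SAP*

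**What the plan says.** SAP 4.3 points to Section 5.1 for the exact outcome definitions: "This TSAP provides clarification on main outcomes listed in CSP Section 5.1.1. A more precise definition is provided in" that section. The lung-density outcome then appears as follows.

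- SAP 5.1: "Absolute change from baseline in lung density based on PD15 adjusted for lung volume (ALD) [g/L/year] (up to week 156".
- Heading in SAP 7.4.1: "Absolute change in lung density decline based on PD15 adjusted for lung volume (ALD) [g/L/year] (up to week 156".
- SAP 5, defining change from baseline for continuous assessments: "post-baseline value at visit k - baseline value".
- SAP 7.4.1, defining the response of the repeated-measures model: "change from baseline for ALD for subject i in subject-group (SG) j at visit k, k = 5, 6, 7". The only fixed effect is a categorical mean for each subject group at each visit, and tests are on least-squares means.

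FEV1 is treated differently. SAP 5.1 calls it "Annual rate of lung function decline based on FEV1 [mL/year] (up to week 156", and SAP 7.4.1 gives it a random intercept and slope model in continuous time, comparing groups through the group-by-time coefficient.

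SAP 7 has a days-to-years rule, introduced by "If applicable, conversion from days to weeks, months and years will be as follows". It names no endpoint.

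In the protocol, Section 5.1.1 describes the outcome as change in CT lung density over the study, with no time denominator. Section 7.7.2 bases CT precision on the SD of annual PD15 decline.

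**The concern.** A quantity in g/L/year is a rate, and a difference between two density values is not. For FEV1 the SAP names a rate and writes a model that estimates one. For lung density it gives the unit of a rate and a model for cumulative change.

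This is the first-listed main outcome of a study of emphysema progression. If the Week 104 and Week 156 means were tabulated under the stated unit, a reader would take two or three years of loss as one year's loss. Steady decline would then look like accelerating decline across the three visits. Differences from the ex-smoking controls would be misread in the same way.

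**Working it through.** **The plan's own annual-scale figure.** Protocol Table 7.7.2: 1 is the place where CT decline is put on a yearly scale. Take n = 100, SD = 5 and half-width h = 1, with t = 1.984 (97.5th percentile on 99 df). The chi-square argument is h²·n(n−1)/(t²·SD²) = 9900/(3.937 × 25) = 100.6. The probability of a half-width of at most 1 is then 0.563, or 0.557 conditional on the interval containing the true mean. The table prints 0.557. It is sound on its own scale and shows that an annual decline was in view at planning. It does not say which quantity the SAP model should estimate.

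**Units in the lung-density model.**

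1. Response: ALD at visit k minus ALD at baseline, so g/L − g/L = g/L.
2. Parameter: τ_jk is the mean of that response in group j at visit k, so it is also in g/L.
3. To reach g/L/year, the response must be divided by elapsed years, or a coefficient on continuous time must be estimated. The visible text of SAP 5, 5.1 and 7.4.1 does neither for ALD.
4. In the FEV1 model, the coefficient on t_ik, (γ + g_i + φ_j), is in litres per unit of time, which is a rate.

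**Size of a misreading.** Inputs are the planned CT days 364, 728 and 1092 with baseline on Day 1 (SAP Table 6.7: 6) and 365.25 days per year (SAP 7). Elapsed years = (planned day − 1)/365.25. Assume a constant loss of r g/L per year.

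| Visit | Elapsed years | Expected visit mean (loss) | Error if read as g/L/year |
|---|---|---|---|
| Week 52 | 363/365.25 = 0.994 | 0.99r g/L | −0.6% |
| Week 104 | 727/365.25 = 1.990 | 1.99r g/L | +99% |
| Week 156 | 1091/365.25 = 2.987 | 2.99r g/L | +199% |

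For example, with r = 1 the Week 156 mean loss is 2.99 g/L. Counting full weeks instead (364, 728 and 1092 divided by 365.25) gives 0.997, 1.993 and 2.990, so the conclusion is unchanged.

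**Dependence on scan timing.** The CT analysis windows are Days 29–546, 547–910 and 911 onward. In elapsed years these are 28/365.25 = 0.08 to 545/365.25 = 1.49; 546/365.25 = 1.49 to 909/365.25 = 2.49; and from 910/365.25 = 2.49. The factors in the table are therefore nominal and hold for scans near the planned days.

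**The case against.** The strongest reply is that this is a labelling slip. The response, visits and model are explicit, so a programmer following the equation computes one thing. All tests are exploratory (Protocol 7.2), and no decision rule in the visible text turns on the unit. That stands as far as it goes: the repeated-measures analysis is well defined. But SAP 5.1 is named as the more exact definition of the main outcomes, and as printed it does not describe what the model estimates.

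Second, SAP 5.3, 7.6 and Section 9 (including 9.2, which defines ALD) are not published, and redacted text is not missing text. This also stands. A reader might infer that the plan contains no route to an annual rate, and the documents do not support that. An annualisation step elsewhere would still leave the printed response and the printed unit in conflict, and a cross-reference would be needed.

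Third, Protocol 7.7.2 suggests that a yearly decline may be the intended quantity, while Protocol 5.1.1 points to cumulative change. So it cannot be assumed that the model is right and the unit wrong.

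Two stronger readings are tempting. One takes the SAP 7.4.1 heading literally, as a change in the rate of decline, which would be a third quantity. The sentence after the heading answers this: it says that change from baseline over time is evaluated. The other is that the planned estimates are themselves wrong by a factor of two or three. They are not. The factor arises only if they are reported or read as yearly rates.

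**Conclusion.** The point holds for the visible text. The printed unit is that of a rate, and the printed model estimates cumulative change at three visits. Which of the two is intended is not settled by the documents.

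The possible overstatement is about 2-fold at Week 104 and 3-fold at Week 156, with Week 52 about right. This rests on four conditions: constant decline, scans near the planned days, visit means reported under the stated unit, and ALD being in g/L, which is itself inferred from the label. Because the study is exploratory, the consequence is for the definition and interpretation of a main outcome, not for a type I error rate. The point merits correction because of the outcome's standing and the small effort needed.

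**What to change.** Make the unit and the model agree in SAP 5.1 and 7.4.1.

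- If the repeated-measures model stays as written, use one wording in both places: *Absolute change from baseline in ALD [g/L] at Weeks 52, 104 and 156*. Drop the word decline from the 7.4.1 heading and label the estimates accordingly. This takes two wording edits, no new data and no change to the model.
- If an annual rate in g/L/year is the intended quantity, name its estimator or cite the section that already contains it. One candidate is the random intercept and slope model already written for FEV1, applied to ALD at Visits 2, 5, 6 and 7 with time taken from actual scan dates. The cost is one further PROC MIXED call and an assumption of linear decline, which the visit means from the existing model can be used to check.

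The same edit can align the FEV1 unit, which is mL/year in SAP 5.1 and L/year in SAP 7.4.1. That is a conversion only.
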